7.4 Antiarrhythmic Drugs

Use of Class I / III AADs during the ADVANTAGE AF Study must be managed carefully.

The terms “Antiarrhythmic Drugs, Class I and III”, “Blanking Period”, “Failed AAD” and “Non-Failed AAD” are defined specifically in **Section 23.2**.

Failed AADs

At the Baseline Assessment, **Section 7.5**, all Class I and III AADs previously used by the subject must be defined as Failed AADs or Non-Failed AADs in the CRF, including for any Failed AADs the maximum failed dose (see **Section 23.2**).

Amiodarone

- May not be used after the Blanking Period or the subject becomes a Treatment Failure.
- If subjects are prescribed Amiodarone, treatment must be stopped by the Day 30 Assessment.

Managing AADs During the Blanking Period

During the Blanking Period the subject should be assessed for AAD continuation. Titration of Class I / III AADs is allowed during the Blanking Period.

To account for the hard cutoff of the Blanking Period at 90 days and given the permitted visit window for the Day 90 Assessment (90 ± 14 days), AADs that are taken during the Blanking Period but are stopped at the time of a within-window Day 90 visit (up to and including Day 104) will not be counted as potential Treatment Failures to allow the necessary physician evaluation.

Managing AADs After the Blanking Period

If indicated, subjects may remain on Class I / III AADs following the Blanking Period, preferably those established as Failed AADs (see **Section 23.2**) at or below the maximum failed dose so as not to create a post-Blanking Period Treatment Failure.

Use of a Non-Failed AAD after the Day 90 Assessment constitutes a Treatment Failure for the primary effectiveness endpoint.

AAD Monitoring

At all subsequent follow-up assessments, subject compliance with, and changes in drugs and daily doses for any Class I / III AAD, will be elicited and recorded.

7.5 Baseline Assessment

Type of Assessment: In-person at investigational site

The completion of the Baseline Assessment requires an in-person assessment. Such assessments must be deferred if this is not possible.

The below baseline data will be generated in the window beginning 30 days prior to the Consent Date and ending on the date of the Index Procedure, unless otherwise specified.

This data will include but is not limited to:

- Demographics including gender, height, and weight, race and ethnicity, in accordance with local requirements⁵
- Pertinent medical and cardiovascular history
- AAD history to establish Failed AAD and Non-Failed AAD status
- Anticoagulation medication history
- Cardiac physical examination
- Pregnancy test (all women of child-bearing potential)
- Hematocrit, hemoglobin, electrolytes, blood urea nitrogen (BUN), creatinine
- COVID-19 testing according to investigation site requirements. The following information is not required if it is not a site requirement, but if available the data should be recorded:
 - A negative PCR for SARS-CoV-2 virus or equivalent testing, or
 - Confirmation of vaccination with a commercially available vaccine

⁵ With a goal of achieving an unbiased estimate of treatment effect in the general population, Boston Scientific seeks to enroll a diverse population including representative proportions of relevant age, racial, and ethnic subgroups, which are consistent with the intended use population of the device. Case Report Forms will collect data on age, race and ethnicity in order to achieve this goal, in accordance with local regulations.

- 12-lead ECG
- Imaging (within the window beginning 180 days prior to the Consent Date and ending on the date of the Index Procedure)
 - TTE or Cardiac CT/ MRI for LA dimensions
 - TTE for LVEF and ventricular wall motion
 - Cardiac CT or MRI establishing cardiac anatomy for mapping and PV dimensions
- NYHA Classification
- National Institutes of Health Stroke Scale (NIHSS) score by NIHSS-certified site personnel
- CHA₂DS₂-VASc score
- Quality of Life Measures:
 - The 3-level EuroQol standardized questionnaire of health states (EQ-5D-3L)
 - The Atrial Fibrillation Effect on QualiTy-of-Life Questionnaire (AFEQT) quality of life assessments
- Only if available, coronary anatomy characterization based on data obtained from previous heart catheterization or CT angiography: left-dominant, right dominant or co-dominant.

7.6 *LUX-Dx Insertion*

A LUX-Dx is required for post ablation rhythm monitoring for all Roll-In and Treatment Subjects. As described in the **Section 5**, subjects with an active LUX-Dx inserted within 6 months of enrollment or an estimated one year or greater of battery life may be considered for participation in ADVANTAGE AF Phase 2. For those subjects enrolled without a pre-existing LUX-Dx ICM, the LUX-Dx insertion must occur after enrollment and within seven (7) days post Index Procedure/Rescheduled Index Procedure. It is highly recommended for the LUX-Dx to be inserted 30 days prior to the Index Procedure to allow collection of baseline arrhythmia assessment. The LUX-Dx insertion shall be performed according to the recommended insertion technique described in the LUX-Dx ICM User's Manual. The study site will collect data associated with the procedure, including printing the LATITUDE Clarity programming report. Subjects enrolled with an active LUX-Dx implanted prior to enrollment in the study must have LUX-Dx programming settings updated, if necessary, in accordance with the initial programming described directly below, and a LATITUDE Clarity programming report printed to document the ICM settings. Enrollment in LATITUDE Clarity can be performed prior to, during, or immediately after the insertion procedure. Subjects should be shown how to use their myLUX patient application to complete manual transmissions when experiencing symptoms, and reminded of the importance to remain connected to the LATITUDE Clarity system throughout the duration of the trial. Subjects who become disconnected from the LATITUDE Clarity system for greater than 7 days should be contacted and notified to reconnect and remain connected through their MyLUX Mobile Patient Device/App.

Initial programming of the LUX-Dx device aligns with all detection algorithm nominal parameters as defined in Table 7.6-1 for Post AF Ablation as the reason for monitoring⁶, in addition to those parameters listed in **Table 7.6-1** below.

⁶The LATITUDE Clarity Alert Settings are associated with the Post AF Ablation reason for management settings with exception of turning on the Alert for AT Events – which is not a nominal setting for “Post AF Ablation” reason for monitoring).

Table 7.6-1: LUX-Dx Initial Parameter Settings

Parameter	Post AF Ablation Setting	Latitude Clarity Alert Setting
AF Detection	On	Alert for AF Event – On
AF Response	More	Yellow Alert
AF Duration	4 min	
Pause Response	Less	Alert for AF Event – On
Tachy Response	Less	Yellow Alert
AT Detection	On	Alert for Tachy Events –
AT Duration	4 hours at 110 bpm	On Red Alert

Any programming outside of these nominal parameters prior to a confirmed recurrence of Detectable AF, AT or AFL must be entered into the EDC and justification provided.

7.7 *Index Procedure / Rescheduled Index Procedure*

7.7.1 *Index Procedure / Rescheduled Index Procedure Data Collection*

Type of Assessment: In-person at investigational site
The performance of the Index Procedure / Rescheduled Index Procedure and the Pre-Discharge Assessment both require an in-person assessment. The Index Procedure / Rescheduled Index Procedure must be deferred if this is not possible.

Procedural data will be collected including but not limited to:

- The results of transesophageal echocardiography (TEE) or volumetric CT within 48 hours prior to procedure, or intracardiac echocardiography (ICE) prior to transseptal puncture, utilized for exclusion of LA thrombus.
- Pregnancy test (all women of childbearing potential if the baseline pregnancy test was obtained more than 30 days prior to the Index Procedure / Rescheduled Index Procedure)
- Documentation of PVI for each attempted vein, of PWI, and if performed, of CTI BDB
- Post-ablation electroanatomical maps, if performed with Rhythmia
- The functional status of both phrenic nerves will be assessed radiographically pre and post ablation.
- Method of sedation or anesthesia
- Whether adenosine was used to confirm PVI and / or PWI
- Whether a post-procedure cardioversion was performed
- Adverse events
- For the 3D mapping system: Manufacturer and model, when applicable
- 12-lead ECGs pre- and post-ablation
- Procedural times
- Ablation data

- Procedural anticoagulation data:
 - For subjects on a DOAC whether DOAC therapy was interrupted for procedure
 - For subjects on warfarin, a pre-ablation international normalized ratio (INR) value
 - Procedural heparin administration and timing
- Device deficiencies and malfunctions

7.7.2 Index Procedure Workflow

This section contains important information regarding the procedures for cardiac ablation specified in Phase 2 of the ADVANTAGE AF Study. Investigators and staff should refer to training materials and the IFU documents as applicable per device.

Ablation under this protocol will generally follow the order below. If performed, CTI ablation should be performed after PVI and PWI. However, the Investigator may alter the ablation sequence if necessary for subject welfare.

Unless otherwise directed by Sponsor, at the conclusion of the procedure, all single-use components of the FARAPULSE PFA System should be returned to the Sponsor.

7.7.2.1 Preparation

Subjects must be screened for substantial compliance with 4 weeks of systemic anticoagulation prior to the Index Procedure and, if in the opinion of the Investigator, this condition has not been met, the subject will be rescheduled as defined in Section 7.7.3.

TEE or volumetric CT within 48 hours of the procedure or ICE during the procedure will be utilized prior to transseptal puncture for exclusion of LA thrombus. If the study reveals atrial thrombus, the investigational procedure will not begin or will be terminated before accessing the left atrium, no ablation will be performed, and the subject will be rescheduled as defined in Section 7.7.3.

Phrenic nerve function will be assessed prior to ablation per Investigator standard of care, preferably by a pre-sedation fluoroscopic sniff test. Subjects will undergo sedation / anesthesia according to institutional protocol. They will then be prepared in conventional sterile fashion for a cardiac catheterization procedure.

Femoral vein access will be obtained aseptically under ultrasound guidance.

Commercially available diagnostic catheters may be placed before or after transseptal access at the Investigator's discretion. Transseptal access to the LA will be obtained using commercially available devices, establishing guidewire access to the LA.

A heparin bolus will be delivered prior to or immediately after transseptal puncture. Procedural ACTs will be monitored according to the investigational site's standard of care and maintained at a minimum of 300 seconds at least until all devices are withdrawn from the left atrium.

Topical anesthetic agents, particularly benzocaine, must not be used for the TEE on the same day as the procedure in order to minimize the likelihood of the development of methemoglobinemia due to polypharmacy, in those subjects that will undergo the nitro administration protocol (Section 7.7.2.5) during CTI ablation with the FARAPPOINT PFA Catheter. Methemoglobinemia is a rare but potentially serious side effect of nitroglycerin, a blood disorder in which there is an abnormal increase in the level of methemoglobin, a form of hemoglobin that cannot carry oxygen effectively.

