¹ Baseline Assessments must be generated in the window beginning 30 days (within 180 days for TTE and cardiac CT / MRI) prior to the Consent Date and ending on the date of the Index Procedure.² Assessments that are defined as remote may also be performed at the investigational site (non-remote) at Investigator discretion and subject agreement.³ Baseline assessments include the inclusion / exclusion criteria and the data stipulated in Section 7.5.⁴ Laboratory tests include hematocrit, hemoglobin, electrolytes, blood urea nitrogen, creatinine and if applicable a pregnancy test at baseline, or for the Index or Re-ablation procedure (if baseline pregnancy test done more than 30 days prior to Index Procedure/re-scheduled procedure)⁵ Within 180 days of Consent Date. Must include baseline ventricular wall motion.⁶ MRI / CT cardiac imaging at baseline within 180 days of Consent Date; subsequently only if required if there is a clinical suspicion of PV stenosis⁷ Performed within 48 hours prior to (TEE or CT) or at the procedure prior to transeptal puncture (TEE or ICE).⁸ Only if resolution of phrenic nerve palsy has not yet been demonstrated.⁹ If NIHSS score has increased by 1 or more points or if there is a clinical suspicion of stroke / TIA, then a consulting neurologist will perform a stroke assessment and include the results of a concurrent brain DW-MRI scan.¹⁰ Re-ablation post-Blanking Period procedure data collection will only include adverse events, gaps identified and ablated and number of applications required¹¹ Required post-ablation for FARAPoint subjects with ischemic changes on their post-ablation 12-lead ECG only¹² Including one pre- and one post-ablation. If the post-ablation 12-lead ECG indicates any changes, an additional 12-lead ECG is required prior to hospital discharge.¹³ Required insertion between enrollment and up to 7 days after the Index/Rescheduled Index Procedure; highly recommended to occur 30 days prior to Index Procedure

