7.7.2.5 CTI Ablation

The following subjects will undergo CTI ablation with the FARAPoint PFA Catheter:

- Required: For subjects with a history of CTI-mediated (typical) AFL and
 - Who have not had a CTI ablation procedure, or
 - Who have had a CTI ablation procedure but have recurrent CTI conduction.
- Required: Subjects who manifest CTI-mediated AFL (spontaneous or induced) during the Index Procedure
- At Investigator discretion: Subject welfare indicates that CTI ablation should be performed.

CTI Ablation with the FARAPoint PFA Catheter will be performed according to the IFU documents and institutional practice. Per the FARAPoint Catheter IFU, no more than two energy applications should be delivered at any given catheter placement. Repeat placement of the FARAPoint Catheter at nearly identical locations should be avoided unless there is a clear clinical need for such placements.

The FARAWAVE Catheter is not allowed to complete any CTI lesion.

CTI ablation with the FARAPoint PFA Catheter must adhere to the following protocol requirements in order to mitigate the risk of coronary spasm during ablation application.

No ablations outside CTI with the FARAPoint PFA Catheter are allowed.

The following prophylactic workflow is required to be followed when CTI ablation is performed with the FARAPoint PFA Catheter:

- **Pre-Treatment (Required)**: Administer a three milligrams (3mg) nitroglycerin IV bolus via the FARADRIVE sheath (or other sheath with central access) approximately one minute prior to the first PFA application at the anterior position of the CTI line.
- **During Ablation (Required)**:

⁷ If anesthesia necessitates, a pre-discharge fluoroscopic sniff test or inspiration / expiration CXR may be acceptable. See **Section 7.8**.

- Depending upon procedure duration and patient condition, administer an additional 2mg IV bolus via the FARADRIVE sheath (or other sheath with central access) approximately two (2) minutes apart until the ablation is complete or a maximum total of 9mg IV of nitroglycerin has been administered.
- If bidirectional block (BDB) is assessed and not present and additional ablation lesions are required in the anterior aspect of the cavo-tricuspid isthmus line, Investigator discretion will determine whether to administer an additional 2-3 mg of nitroglycerin IV via the FARADRIVE sheath (or other sheath with central access) prior to re-ablation.

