Adjustments to the nitroglycerin dosing protocol defined above are allowed per Investigator discretion based on patient condition, but the rationale for any changes to the defined workflow will be collected. Failure to administer any pre-treatment nitroglycerin will be a protocol deviation.

Vasopressors may be administered per physician discretion given that comorbidities, drug regimens, mode of anesthesia, and baseline blood pressure will vary among subjects.

200 micrograms (μ g) of phenylephrine should be administered prior to the first dose of nitroglycerin. If not administered, the rationale will be collected.

Additional vasopressor doses may be administered at the discretion of the physician depending upon the blood pressure response to nitroglycerin. Investigators may choose to administer a different vasopressor depending upon the clinical profile of the subject. All medications administered during the procedure, dose, route and timing of administration in relation to the PFA applications will be recorded.

For those subjects with a known left dominant coronary artery system, as defined by a left heart catheterization or coronary CT angiography, the above prophylactic nitroglycerin workflow is not required. The proximity of the catheter to the artery may be directly visualized in real-time via intracardiac echocardiography. Routine hemodynamic monitoring for patients undergoing sedation and cardiac ablation is recommended.

A post-procedure 12-lead ECG will be recorded following CTI ablation to assess absence of ischemia. If the post-procedure ECG shows any ischemic changes, a transthoracic echocardiographic assessment is **required** the same day as the procedure to assess if intraventricular wall motion abnormalities are observed compared to the pre-procedure echocardiographic assessment (Section 7.8).

After CTI ablation is completed, BDB will be assessed, and if necessary, additional applications may be performed until BDB is confirmed. The CTI ablation data will be documented in the CRF.

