7.7.2.6 Other Ablations for Atrial-Dependent Arrhythmias

When the Investigator determines that subject welfare requires intervention for either an accessory pathway, AVNRT or spontaneously occurring treatment-emergent AFL or AT, ablation for these arrhythmias may be performed using any commercially available RF ablation catheter. These ablations must not be performed with the FARAPULSE PFA System and should be performed after all ablation with the FARAPULSE PFA System is complete. These permitted ablations and the associated data will be documented in the CRF and do not constitute Persistent AF Acute Procedural Failure. FARAWAVE usage is not allowed to complete any lesion outside of the PVs and LAPW, as described in the IFU.

Ablation for an arrhythmia that is provoked only by catheter manipulation or is only inducible by pacing or pharmacologic stimulation is not permitted.

IMPORTANT: FARAWAVE cannot be used to complete any lesion in the Left Atrium except for the PVs and LAPW, under any circumstances.

FARAWAVE cannot be used in any other location, including the right atrium or either ventricle!

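### Appendix A 7.7.2.1 bans topical anesthetic for a same-day TEE only in subjects who will receive nitroglycerin, but 7.7.2.5 can first require nitroglycerin after that TEE

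*Combined protocol and SAP*

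**What the plan says.** All references are to Appendix A (Phase 2).

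- **7.7.2.1 Preparation** requires left atrial thrombus to be excluded before transseptal puncture, by TEE or CT within 48 hours or by ICE in the procedure. Footnote 7 of Table 7.2-1 also allows the TEE at the procedure itself. 7.7.2.1 then forbids topical anesthetics for a TEE on the procedure day "in those subjects that will undergo the nitro administration protocol (Section 7.7.2.5) during CTI ablation" with FARAPOINT. The stated reason is to lower the chance of methemoglobinemia from combined drugs.
- **7.7.2 Index Procedure Workflow** sets the order: "If performed, CTI ablation should be performed after PVI and PWI". The investigator may change it for subject welfare.
- **7.7.2.5 CTI Ablation** lists who must have FARAPOINT CTI ablation, including: "Required: Subjects who manifest CTI-mediated AFL (spontaneous or induced) during the Index Procedure". A 3 mg nitroglycerin bolus is required about a minute before the first application on the anterior part of the line. The one stated exemption from the nitroglycerin workflow is known left-dominant coronary anatomy. Two sentences govern departures: "Adjustments to the nitroglycerin dosing protocol defined above are allowed per Investigator discretion based on patient condition", and "Failure to administer any pre-treatment nitroglycerin will be a protocol deviation".
- **4.1.2 and 4.2** provide for pre-screening against the CTI criteria, for Roll-In Subjects only.
- **16.6** asks sites to have co-oximetry and methylene blue available for subjects in the nitroglycerin workflow.

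**The concern.** The ban is the step meant to stop two drugs that can each cause methemoglobinemia from being given on the same day. It depends on whether the subject will receive nitroglycerin. For a subject with no flutter history, the team may not know this when the TEE probe goes in. If CTI-mediated flutter then appears, the operator has no instruction. Giving nitroglycerin creates the combination that 7.7.2.1 seeks to avoid. Giving none before treatment is a protocol deviation and removes the prophylaxis against coronary spasm.

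What is at stake is the safety of a few subjects and clear direction for the operator.

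**Working it through.** The point rests on the order of steps. The plan states no figure to reproduce.

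**Order of events for a Treatment Subject without flutter history**

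1. A TEE is done on the procedure day, before transseptal puncture (7.7.2.1; Table 7.2-1, footnote 7). No CTI ablation is planned, so the ban does not visibly apply, and a topical agent may be used.
2. PVI and PWI follow.
3. CTI-mediated flutter appears or is induced. FARAPOINT CTI ablation becomes required (7.7.2.5).
4. Nitroglycerin pre-treatment becomes required with it, unless left dominance is known (7.7.2.5).

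The condition for the ban can therefore first become true at step 3, after the act it governs at step 1.

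**Does other text close the gap?**

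- *Radiofrequency route.* Section 7.7.2.6 says that for "spontaneously occurring treatment-emergent AFL or AT, ablation for these arrhythmias may be performed using any commercially available RF ablation catheter". This is an arguable way out for spontaneous flutter. It does not cover induced flutter, because the same section adds: "Ablation for an arrhythmia that is provoked only by catheter manipulation or is only inducible by pacing or pharmacologic stimulation is not permitted". Section 7.7.2.5, in contrast, requires FARAPOINT for induced CTI-mediated flutter. Under 3.5.2, using another modality for CTI-mediated flutter counts as a CTI acute procedural failure, a descriptive endpoint.
- *Dose adjustment.* The investigator may reduce nitroglycerin, but nothing links this to topical exposure that day.
- *Co-oximetry and methylene blue (16.6), and the methemoglobinemia item among the additional safety endpoints (3.5.1).* These diagnose, treat or count after exposure.
- *Pre-screening.* It covers Roll-In Subjects, so they are outside this point. Treatment Subjects are not pre-screened in this way.

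**Size**

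Inputs from 4.1.2: 258 Treatment Subjects, about 30% expected to receive FARAPOINT, an estimated 80, and no upper limit.

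- Expected FARAPOINT subjects: 0.30 × 258 = 77.4. The estimate of 80 is 80 / 258 = 31.0%, which agrees.
- Affected subjects = N × a × b. Here N is the number of FARAPOINT subjects, a the share whose flutter is first seen in the procedure, and b the share of those with a same-day TEE under a topical agent. The documents give neither a nor b.

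Purely as assumptions, take a from 5% to 50%, b from 10% to 50%, and N = 80:

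| a | b | N × a × b |
|---|---|---|
| 5% | 10% | 0.4 |
| 10% | 25% | 2.0 |
| 50% | 50% | 20.0 |

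Known left dominance would lower each figure. FARAPOINT use above 80 would raise it.

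**Reach of a wider ban**

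Treatment Subjects who never receive FARAPOINT: 258 − 80 = 178 (69.0%), or 258 − 77 = 181 (70.2%). Only those having a same-day TEE would be affected.

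**The case against.** The strongest reply is that the rule is defined by outcome. It speaks of subjects who will undergo the nitroglycerin protocol, not of those planned for it. On that reading, anyone who has topical anesthetic that day and later receives nitroglycerin is inside the ban, and a careful site complies by never using a topical agent for a same-day TEE. The reading is fair, but a site must work that precaution out for itself. A rule that turns on a fact unknown at the time of the act cannot reliably prevent the act.

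The second reply is rarity. Four conditions must coincide, the protocol itself describes methemoglobinemia as rare, and ICE, which 7.7.2.2 recommends for these procedures, avoids the issue. This stands and limits the severity.

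The third is that 7.7.2 sends staff to the instructions for use and training materials. Those were not available and may deal with topical exposure. This also stands.

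Two stronger inferences are tempting and are not supported:

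- A reader might infer that the TEE rule is the only nitroglycerin-related protection that depends on CTI ablation. Only the enrollment exclusions in 5.3 are unconditional (nitroglycerin reaction, phosphodiesterase inhibitors, congenital methemoglobinemia, G6PD deficiency). Co-oximetry and methylene blue (16.6) and phenylephrine (7.7.2.5) are also tied to nitroglycerin use.
- A reader might infer that the 9 mg nitroglycerin maximum can be exceeded, because 7.7.2.5 allows a discretionary further dose if block is absent. The text does not say whether that dose falls within the maximum, and the question has no bearing on the timing of the TEE.

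**Conclusion.** The gap is real and minor. For Treatment Subjects who have a same-day TEE with a topical agent, whose CTI-mediated flutter is first seen in the procedure and who have no known left-dominant anatomy, the protocol does not secure its own preventive step. It also does not say what to do next. Their number cannot be derived from the documents, is probably very small and may be near zero. The 0.4 to 20 range rests wholly on assumed shares.

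The conclusion assumes the normal order of steps in 7.7.2 and that no unseen document fills the gap. It does not extend to discretionary CTI ablation, Roll-In Subjects, known left dominance, or sites using CT, ICE or a TEE on a preceding day. Power, type I error and the primary analyses are unaffected.

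**What to change.** Reword 7.7.2.1 to this effect: *No topical anesthetic, benzocaine in particular, is to be used for a TEE on the procedure day in any Phase 2 subject, unless a left-dominant coronary system is documented and nitroglycerin is not planned.* Name the alternatives already allowed: CT within 48 hours, ICE, or a TEE on a preceding day within 48 hours.

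The cost is one sentence and a site letter, with the ethics review that Appendix A 14.1 requires for such an amendment. The downside is that subjects having a same-day TEE who never receive FARAPOINT, some of the 178 to 181 above, would lose topical anesthesia. That group shrinks if FARAPOINT use exceeds 80.

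A narrower alternative is one sentence in 7.7.2.5 on how to proceed if a topical agent was already used that day. It would manage the situation but not prevent it.
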